^c After end of study, serious adverse events suspected to be related to investigational product will be reported to Amgen. Please refer to Section 8.3.4.1.3 for additional details.

^d On day 43, investigational product administration and assessments which are to be completed prior to investigational product administration, will be completed at the study site. Visit for pharmacokinetic blood sample collection may be performed as a home health visit. In addition to collection of pharmacokinetic blood samples, adverse events, serious adverse events, and concomitant medications review will be conducted.

^e For women of childbearing potential only: serum pregnancy test is to be performed at screening (central laboratory) and urine pregnancy test is to be performed at all other indicated time points (local laboratory). To determine if follicle-stimulating hormone (FSH) level should be assessed, refer to the definition of postmenopausal female provided in Section 11.5.

^f A subject's anti-dsDNA will be tested with a consistent assay throughout the study.

^g Clean catch urine specimen required and urine protein/creatinine ratio will be calculated.

^h Must be completed by a health care provider before assessing the hSLEDAI and BILAG scores.

ⁱ To be taken predose.

^j A single pharmacokinetic blood sample will be collected between 6 and 24 hours postdose week 6 and another pharmacokinetic sample will be collected between 48 and 96 hours postdose week 6. These samples may be collected as part of a home health visit.

[figure not shown]
^k At visits on which investigational product is administered, all assessments are to be completed in advance of investigational product administration unless otherwise noted. The dose of investigational product must be given within \pm 5 days of the scheduled time point. If that window is missed, that dose will not be administered, and the next dose will be administered at the next scheduled dosing date. Any 2 consecutive doses of investigational product must be at least 7 days apart.

Table 1-4. Schedule of Activities – Safety Follow-up/week 56 Visit

	Safety Follow-up Visit (Weeks)
Week ± Visit Window (days)	56 weeks +5 days^a
Vital signs	X
Adverse events	X
Serious adverse events ^b	X
Concomitant medications review	X
LABORATORY ASSESSMENTS	
Urine pregnancy test	X
Hematology	X
IMMUNOGENICITY	

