- Remove specific reference to Phadia assay in order to allow for regional differences in the assay for anti-double stranded DNA (Section 1.3, Section 5.1 [criterion no. 103], and Section 8.3.3.1).

- Update exploratory endpoints (Section 3) to:
 - [REDACTED]
 - [REDACTED]
- Update inclusion criterion no. 103 to include anti-Smith test.
- Update exclusion criteria (Section 5.2) to:
 - Update exclusion criteria for active infection prior to screening (from 4 weeks to 2 weeks) (criterion no. 205).
 - Include “presence of anti-cyclic citrullinated peptide [anti-CCP] and rheumatoid factor OR current history of RA (rheumatoid arthritis) OR presence of erosive arthritis on imaging” as example of diagnosis of any chronic inflammatory disease other than systemic lupus erythematosus (criterion no. 232).
 - Include tyrosine kinase inhibitor as prohibited medication during the study (criterion no. 237).
 - Add a new criteria to state that female subjects of reproductive potential must agree not to donate eggs during the study and for 6 weeks after receiving the last dose of investigational product (new criterion no. 239).
- Refer to auxiliary medicinal product, in accordance with EU-CTR (Section 6).
- Clarify that samples testing positive for anti-efavaleukin antibodies will also be tested for neutralizing antibodies (Section 8.7).
- Include minor language updates in Biomarker Development and Future Research sections to align with current protocol template version 29.0, effective date 25 May 2022 (Section 8.8.2 and Section 8.8.3).
- Minor updates in the list of references (Section 10).
- Minor updates in the list of abbreviations (Section 11.1).
- Make administrative and editorial changes throughout the protocol for clarification.

Amendment 3

Protocol Title: A Phase 2b Dose Ranging Study to Evaluate the Efficacy and Safety of Efavaleukin Alfa in Subjects with Active Systemic Lupus Erythematosus With Inadequate Response to Standard of Care Therapy (VIOLET)

Amgen Protocol Number Efavaleukin alfa (AMG 592) 20200234

NCT04680637

Amendment Date: 21 October 2022

Rationale:

This protocol has been amended to:

- Add back the requirement for an independent blinded joint evaluator to conduct joint count assessments (number of tender and swollen joints). In the recently approved protocol amendment 2, this requirement was removed, and it needs to be re-incorporated to ensure consistency of the evaluation of this parameter in the trial.

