### Anti-dsDNA

**Anti-dsDNA is categorized as negative, indeterminate or positive as follows:**

**Positive:** > 15 IU/mL for subjects in Asia (Japan, Hong Kong, Taiwan and South Korea) and > 75 IU/mL for all other subjects.

**Indeterminate:** 10 - 15 IU/mL for subjects in Asia (Japan, Hong Kong, Taiwan and South Korea) and 30 - 75 IU/mL for all other subjects.

**Negative:** < 10 IU/mL for subjects in Asia and < 30 IU/mL for all other subjects.

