## **9. Statistical Methods of Analysis**

### **9.1 General Considerations**

All categorical variables will be summarized using the number and percent of subjects falling into each category and all continuous variable will be summarized using mean, standard error (SE), standard deviation (SD), median, first quartile (Q1), third quartile (Q3), minimum, maximum, and number of subjects with observations. Safety endpoints will be summarized descriptively, including treatment-emergent adverse events and serious adverse events, clinically significant changes in laboratory values and vital signs, and incidence of antidrug antibodies. All safety analyses will be performed using the Safety Analysis Set based on subject's actual treatment received.

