### **9.4 Demographic and Baseline Characteristics**

The following demographic, baseline characteristics, baseline disease characteristics and baseline therapies of interest will be summarized descriptively by randomized treatment group.

Demographics:

- sex (female, male)

- age (years)
- age groups ( $\geq 18$  to  $< 50$ ,  $\geq 50$  and  $18 - 64$ ,  $65 - 74$ ,  $75 - 84$ )
- race (American Indian or Alaska Native, Asian, Black or African-American, Native Hawaiian or Other Pacific Islander, White, Other)
- ethnicity (Hispanic or Latino, Not Hispanic or Latino)
- geographic region (North America [Canada and United States] + Western Europe [Austria, France, Switzerland] + Asia Pacific [Hong Kong, Japan, South Korea and Taiwan], ROW [Bulgaria, Chile, Colombia, Greece, Italy, Mexico, Poland, Russia, Spain and Turkey])

Baseline characteristics:

- height (cm)
- weight (kg)
- body mass index (BMI) ( $\text{kg}/\text{m}^2$ )

Baseline disease characteristics:

- years since SLE diagnosis
- hSLEDAI score (continuous,  $< 10$  or  $\geq 10$ )
- baseline hSLEDAI organ involvement (CNS [seizure, psychosis, organic brain syndrome, visual disturbance, cranial nerve disorder, lupus headache, cerebrovascular accident], vascular [vasculitis], renal [urinary casts, hematuria, proteinuria, pyuria], musculoskeletal [arthritis, myositis], serosal [pleurisy, pericarditis], dermal [rash, alopecia, mucosal ulcers], immunologic [low complement, increased DNA binding], constitutional [fever], hematologic [thrombocytopenia, leukopenia])
- baseline BILAG domain score (A, B, C, D, E)
  - constitutional
  - mucocutaneous
  - neuropsychiatric
  - musculoskeletal
  - cardiorespiratory
  - gastrointestinal

- ophthalmic
  - renal
  - haematological
- CLASI activity score (continuous, 0, > 0 to < 8,  $\geq 8$ )
- total swollen and tender joint counts
- hand and wrist swollen and tender joint counts
- PGA VAS score
- baseline biomarkers
  - antinuclear antibody ( $\geq 1:80$  vs. negative or  $< 1:40$ )**
  - anti-dsDNA (continuous, positive, indeterminate or negative)**
  - C3, C4 complement (continuous, low or normal/high, low C3 or C4 vs. normal/high C3 and C4)**
  - anti-dsDNA and complement**
    - anti-dsDNA positive and low complement**
    - anti-dsDNA positive and normal/high complement**
    - anti-dsDNA indeterminate and low complement**
    - anti-dsDNA indeterminate and normal/high complement**
    - anti-dsDNA negative and low complement**

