#### **9.7.1 Analyses of Pharmacokinetic Endpoints**

**Amgen Clinical Pharmacology Modeling and Simulation (CPMS) group will conduct PK analysis. Serum concentration data will be summarized by treatment for each PK sampling time point. PK parameters may be summarized if adequately estimated.**

**The descriptive statistics for absolute change from baseline, percentage change from baseline and ratio to baseline will be provided by treatment arms at specified time-points for the endpoints C3, C4, anti-dsDNA antibody and antiphospholipid**

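### Raw anti-dsDNA levels and absolute changes are pooled by arm over two cutoff groups that appear to use different assay scales, so these summaries partly reflect each arm's regional assay mix

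*SAP*

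**What the plan says.** SAP 5.6 (Anti-dsDNA) uses one set of cutoffs for four Asian countries and another for everyone else. Positive is "> 15 IU/mL for subjects in Asia (Japan, Hong Kong, Taiwan and South Korea) and > 75 IU/mL for all other subjects". Negative is "< 10 IU/mL for subjects in Asia and < 30 IU/mL for all other subjects". Values in between are indeterminate.

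The SAP does not name the assays. The protocol gives the likely reason for the split: the Amendment 4 summary of changes says a named assay was removed "to allow for regional differences in the assay for anti-double stranded DNA". Footnotes to Tables 1-2 and 1-3 (Protocol 1.3) add that "A subject's anti-dsDNA will be tested with a consistent assay throughout the study".

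The continuous values are handled without this split:
- SAP 9.4 lists the baseline variable as "anti-dsDNA (continuous, positive, indeterminate or negative", by randomized group.
- SAP 9.7.1 states that "The descriptive statistics for absolute change from baseline, percentage change from baseline and ratio to baseline will be provided by treatment arms", and the list that follows reads "for the endpoints C3, C4, anti-dsDNA antibody and antiphospholipid" antibody.
- SAP 9.1 fixes the statistics: "all continuous variable will be summarized using mean, standard error (SE), standard deviation (SD), median", with quartiles and range.

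No visible text splits, rescales or normalises the raw values by assay or country. The only region subgroup (SAP 4.2) covers the primary endpoint alone and merges Asia Pacific with North America and Western Europe.

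**The concern.** The SAP applies country-specific cutoffs when it classifies subjects and drops the distinction when it averages them. Under its own rules a reading of 20 IU/mL is positive in Japan and negative in Canada. A mean over both kinds of reading lies on neither scale, and the median and quartiles come from the same mixture.

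A pooled mean also moves with the share of Asian subjects in the arm. Protocol 6.4.1 stratifies by region, but the four Asian countries (listed as Asia Pacific in SAP 9.4) are only part of one stratum, so stratification does not control that share. A reader who sees arms differ in mean anti-dsDNA, or in its mean fall, could not tell how much is biology and how much is assay mix. In a study stopped for futility, the descriptive tables are the main output.

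**Working it through.** The plan states no figure for this point, so there is nothing to reproduce. The check takes the cutoffs from SAP 5.6 and adds labelled assumptions.

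**1. Are the scales proportional?**
- Positive cutoffs: 75 / 15 = 5.0.
- Negative cutoffs: 30 / 10 = 3.0.

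If the cutoffs mark comparable points, no single multiplier aligns the two scales.

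**2. Mean level.** Assume every subject sits exactly at their own positivity cutoff, and let f be the share of an arm on the Asian cutoffs. The documents do not give f.

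Arm mean = 15f + 75(1 − f) = 75 − 60f.

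| f | Mean level (IU/mL) | Mean absolute change if all values halve | Percent change |
|---|---|---|---|
| 0% | 75 | −37.5 | −50% |
| 10% | 69 | −34.5 | −50% |
| 20% | 63 | −31.5 | −50% |
| 30% | 57 | −28.5 | −50% |
| 40% | 51 | −25.5 | −50% |

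Arms at 10% and 30% differ by 69 − 57 = 12 IU/mL in level and by 34.5 − 28.5 = 6 IU/mL in absolute change, with identical disease. Percent change and ratio to baseline (0.5) are the same in both arms.

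**3. How much imbalance could chance produce?** Assume 26 subjects per arm: 104 at the third interim analysis (SAP Table 3-1) divided by 4, taking allocation as equal. The SD of the difference in f between two arms is √(2f(1 − f)/26), and each unit of f is worth 60 IU/mL.
- f = 10%: SD 0.083, 95% range ±1.96 × 60 × 0.083 ≈ ±10 IU/mL.
- f = 20%: SD 0.111, ≈ ±13 IU/mL.
- f = 30%: SD 0.127, ≈ ±15 IU/mL.

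With f = 20% overall, a 20-point gap is 0.20 / 0.111 ≈ 1.8 SD, about a 7% two-sided event for any one pair of arms. Step 2 is therefore an uncommon draw, not a typical one.

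**4. How well are the relative measures protected?** Each subject keeps one assay, so a constant factor cancels in a ratio. The protection is not exact, because the scales are not proportional. If the cutoffs did correspond, a fall from the positive to the negative cutoff would be 15 to 10 (change −5, ratio 0.67) on one scale and 75 to 30 (change −45, ratio 0.40) on the other. The absolute changes differ nine-fold and the ratios by a factor of 1.7.

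**The case against.** Several objections have force.

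- **Randomisation.** Assay group is not stratified, but subjects are still randomised, so the mix is balanced in expectation. This stands: what remains is mainly chance imbalance. One qualification is that allocation among the active doses may change after interim analyses (SAP 3.3). If Asian enrolment was uneven over time, the mix could then differ between doses by more than chance. Enrolment timing is not given, so this is only a possibility.
- **Protected summaries are already planned.** SAP 9.7.1 includes percent change and ratio to baseline, and SAP 9.4 includes the country-specific categories at baseline. This stands and limits the point to raw level and absolute change.
- **Two assays are inferred.** SAP 5.6 names none. SAP Section 1 cites Amendment 3 as its basis, whereas the regional-assay rationale is in Amendment 4. The inference is strong, since different IU/mL cutoffs by country otherwise have no visible explanation, but it remains an inference.
- **The illustration has no between-subject spread.** The 12 IU/mL cannot be set against the SD that the table would report. The arms may also exceed 26 subjects, which would shrink chance imbalance.
- **Redaction.** The exploratory endpoints and SAP Table 9-3 are blank in the public text, and SAP 9.7.3 allows further biomarker analyses. A split by assay could sit there.

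A reader might infer that the pooled tables are uninterpretable, or that efficacy is contaminated. The documents support neither. SAP Section 10 removes treatment comparisons at the final analysis, and anti-dsDNA level is not a listed primary or secondary endpoint. Its route into SRI-4 is the hSLEDAI DNA-binding item, which SAP Appendix B scores against the testing laboratory's own normal range.

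**Conclusion.** The point holds in a limited form. As written, the SAP pools raw anti-dsDNA level and absolute change over two cutoff groups that very probably use different scales, so those summaries depend partly on each arm's regional mix.

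The size cannot be computed, because the Asian share and the spread of values are not given. The figures of 12 and 6 IU/mL assume every subject at the positivity cutoff, a uniform halving, and shares of 10% and 30%. With 26 per arm and an overall share of 10% to 30%, chance alone would give a 95% range of about ±10 to ±15 IU/mL for the difference in mean level under the same assumption.

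It would be wrong to read the 5-fold positivity ratio as a conversion factor, since the negative cutoffs differ only 3-fold. The baseline categories and SRI-4 are unaffected by the pooling, and percent change and ratio to baseline are largely protected. This is a minor matter of presentation in descriptive tables, worth correcting because it is cheap.

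**What to change.** In SAP 9.4 and 9.7.1, state that continuous anti-dsDNA level and absolute change are presented separately for the two cutoff groups already defined in SAP 5.6. Use ratio to baseline or percent change, together with the positive, indeterminate and negative categories, as the pooled summaries. Showing the ratio by group in the same table would let a reader see whether pooling it is reasonable.

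Do not rely on multiples of the positivity cutoff to put everyone on one scale, because the two cutoff ratios show that this would align the scales at one point only.

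The cost is a sentence in each section and one by-group in the affected tables. No new data are needed. The drawback is small cells for the Asian group, where quartiles and SDs may be unstable.

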### 5.7 Patient-reported Outcome (PRO) Assessments

#### Medical Outcomes Short Form-36 Questionnaire Version 2 (SF36v2)

The SF-36v2 (acute version) Health Survey (Ware et al, 2000) contains 36 items and is a revised version of the SF-36 Health Survey. The SF-36v2 acute version is a patient reported generic measure of health status. This survey yields assessments of 8 domains of health-related quality of life: 1) limitations in physical activities because of health problems; 2) limitations in social activities because of physical or emotional problems; 3) limitations in usual role activities because of physical health problems; 4) bodily pain; 5) general mental health (psychological distress and well-being); 6) limitations in usual role activities because of emotional problems; 7) vitality (energy and fatigue); and 8) general health perceptions. The scores from the 8 domains will be evaluated independently and aggregated into 2 norm-based summary component measures of physical and mental health. The recall period is the past 7 days. The scoring of SF-36v2 will be processed by QualityMetric's PRO CoRE Software.

#### Patient-Reported Outcome Measurement Information System Fatigue Short Form 7a Instrument (PROMIS Fatigue SF 7A v1.0)

The PROMIS Fatigue Short Form 7a is a 7-item instrument originally constructed by the PROMIS Fatigue team to represent the range of the fatigue trait (PROMIS Fatigue Scoring Manual). It assesses the experience of fatigue as well as its impact on physical, mental and social activities. Both psychometric properties and clinical input were used in the development of the short form from the PROMIS item bank. Estimates of responsiveness and minimally important differences have been reported for the 4 item PROMIS Fatigue instrument in SLE patients (Katz et al, 2019). The PROMIS Fatigue

has also been able to differentiate disease activity in other rheumatologic diseases. (Wohlfahrt et al, 2019),

Details of the scoring algorithm are described in [Appendix C](#).

[figure not shown]
### **LupusQoL Score**

The LupusQoL is the US version of the 34-item PRO originally developed in the United Kingdom (McElhone et al, 2007) for use in adults. This is a SLE-specific health-related quality of life instrument. The LupusQoL consists of 8 domains: physical health (8 items), pain (3 items), planning (3 items), intimate relationships (2 items), burden to others (3 items), emotional health (6 items), body image (5 items), and fatigue (4 items). The final instrument has demonstrated good internal reliability (Cronbach's 0.88 to 0.95), good test-retest reliability ( $r$  0.72 to 0.93), good concurrent validity with the comparable domains of the SF-36 ( $r$  0.71 to 0.79) and good discriminant validity for different levels of disease activity, measured by BILAG index, and damage (Systemic Lupus International Collaborating Clinics/ACR damage index) but not for all domains. The instrument also has acceptable ceiling effects and minimal floor effects.

Details of the scoring algorithm are described in [Appendix C](#).

### **Symptom Questionnaire**

The Symptom Questionnaire is a new patient reported outcome instrument to evaluate inflammatory symptoms, non-inflammatory symptoms, and flare (Pisetsky et al, 2019). The items are based on a 11-point numerical rating scale, with 1 item being a choice of yes or no, all with a 7-day recall. Response to therapy and psychometric properties of the questionnaire will be evaluated with data derived from this study.

## 6. Analysis Sets

### 6.1 Full Analysis Set

The Full Analysis Set (FAS) includes all randomized subjects. Data will be analyzed based on randomized treatment assignment.

### 6.2 Safety Analysis Set

The Safety Analysis set includes all randomized subjects who received at least 1 dose of investigational product. Data will be analyzed according to actual treatment received.

### 6.3 Interim Analyses Set(s)

The Interim Analyses Sets include all subjects randomized on or before the interim analyses cutoff dates, and had the opportunity to complete week 16 (actual week 16 visit date  $\leq$  the cutoff date, or randomization date + 126 -1 < the cutoff date). The interim data cutoff dates are based on the number of subjects having the opportunity to complete week 24 visit presented in [Table 3-1](#).

## 7. Planned Analyses

### 7.1 Interim Analysis and Early Stopping Guidelines

Interim analyses will be conducted to inform adaption of the randomization ratio to enroll future subjects to the 3 efavaleukin alfa treatment groups, holding the allocation to placebo constant at 25%, and to assess efficacy for early futility or administrative success decisions:

- Data will be subject to ongoing checks for integrity, completeness and accuracy in accordance with the Data Management Plan with the expectation that outstanding data issues are resolved ahead of the snapshot to the extent possible. All available data up to and including the data cut-off date will be included in the analysis based on an “as-is” snapshot of the database without data locking.
- The study team, investigators, and subjects will remain blinded to the results of the IAs unless futility is determined.
- The first IA will be executed after the first 40 subjects are randomized and have had the opportunity to complete the week 24 assessment. Subsequent IAs are scheduled after every additional 32 subjects are randomized and have had the opportunity to complete the week 24 assessment until full enrollment. The last IA will occur when all 320 subjects are randomized and have had the opportunity to complete the week 24 assessment. This IA will be referred to as the ‘all-subjects-week-24 IA’.
- Efficacy analyses will be performed at the IAs to assess the likelihood of each efavaleukin alfa treatment group being superior to placebo by a clinically meaningful difference.
  - From the second IA until before the last IA, if this likelihood is unacceptably low for all dose levels, the trial is recommended to stop for futility.
  - At the ‘all-subjects-week-24 IA’, if this likelihood is sufficiently high with at least 1 efavaleukin alfa dose level, the IA triggers an administrative success signal. This would not alter ongoing or planned activities of this phase 2b study, but downstream planning for subsequent trials (e.g., a phase 3 study) may commence. Analysis planned each IA are listed in **Table 3-1. This interim analysis was cancelled due to the study being terminated for futility prior to the enrollment trigger for this analysis.**

At IAs:

- For all IAs before full enrollment, the randomization ratio to each active treatment group is proportional to the posterior probability that each group has the highest response rate among the three active treatment groups with power scale of 2.

$$Allocation_d \propto \Pr \left( p_{d,52} = \max_c p_{c,52} \mid \text{Interim Data} \right), c, d \in \{low, medium, high\}$$

where  $p_{d,52}$  is the posterior probability of achieving SRI-4 response for group d, calculated using a Bayesian independent logistic model with non-informative priors.

- From the second IA until before the last IA, interim futility analysis will be performed based on the Bayesian Hierarchical Model (BHM) as described in the primary efficacy analysis. Enrollment to the study may be stopped for futility if the posterior probability of achieving a clinically meaningful difference in SRI-4 response rates of at least 15% between each active treatment group and placebo is below 2.5% for all 3 efavaleukin alfa doses.

$\max \Pr(p_{d,52} - p_{placebo,52} > \delta \mid \text{Interim Data}) < 0.025, d \in \{\text{low, medium, high}\}$   
where  $\delta = 0.15$  and  $p_{d,52}$  is the posterior probability of achieving SRI-4 response for group d, calculated using a BHM.

- The futility rule and the administrative success trigger are made using estimates of the response rate  $p_{d,52}$  for each dose. However, due to the covariate adjustment, the Bayesian models provide estimates of  $p_d \mid Z$ , the response rate in each dose conditional on the stratification factor Z. The population level estimate for each dose is obtained using a weighted average of the response rate in each stratification group.

$$p_d = \sum_{Z \in Z} w_Z \cdot p_d \mid Z \quad \text{for } d \in \{\text{placebo, low, medium, high}\}$$

The set Z indicates the four possible stratification combinations (hSLEDAI stratification [ $\geq 10$ ,  $< 10$ ] and region [North America + Western Europe + Asia Pacific vs ROW]). The weights  $w_Z$  will be set equal to the observed proportion of patients in each stratification group at the time of the analysis.

- To address the challenge of the lag time between randomization and the week 52 outcome in the adaptive design, a longitudinal model is used to impute week 52 outcome for subjects not yet complete week 52 using their week 16, week 20, or week 24 response data.

